7.5.3. Safety Population

The SAFT Population will be used for safety analysis and will consist of all randomized subjects who received treatment with the IP and will be analyzed as per treatment received. The SAFT population will be the primary population for safety analyses.

Version 1.1 31-May-2023 Confidential Page 20/58

7.6. Sample Size Considerations

This study is not powered for inferential analyses. Approximately 150 subjects will be randomized to the study, 50 subjects in each of the three treatment arms; 20U onabotulinumtoxinA, 20U prabotulinumtoxinA and 40U prabotulinumtoxinA. Assuming 50 subjects per treatment group, exponential distributions for failure and censoring times, a median duration of effect of 4 months in the reference group, and an annual censoring rate of 10%, the study will have 80% power to detect a hazard ratio of 0.47 based on a one-sided hypothesis test of the primary effectiveness endpoint with alpha = 0.025. As such, it is the opinion of the study Sponsor that 50 subjects per group (total sample size n=150) will be sufficient to address the objectives of this study.

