### 4 STUDY DESIGN AND TREATMENT

#### 4.1 Study Design

The study is a multicenter, prospective, randomized, double-blind, active-controlled, single-treatment, increasing dose design.

Up to one hundred and fifty subjects will be randomized 1:1:1, to either 20U onabotulinumtoxinA, 20U prabotulinumtoxinA-xvfs, or 40U prabotulinumtoxinA-xvfs. Subjects with moderate or severe glabellar lines at maximum frown on the 4-point validated Glabellar Line Scale (*GLS*, 0=none, 1=mild, 2=moderate, 3=severe), as judged by the investigator and the subject, will be eligible. See Section 5 for a full description of the inclusion and exclusion criteria.

Safety and effectiveness will be assessed on days 3, 7, and 30, then every 30 days up to 365 days or until the subject has returned to Baseline as assessed by the Investigator, at which point the subject will exit the study.

Duration of effect will be estimated by Kaplan-Meier analysis and will be based on the number of days from Treatment Day (Baseline) to the day that GLS severity (Investigator assessment) at maximum frown returns to the Baseline value (i.e., the treatment will be considered to remain effective for the amount of time during which GLS severity at maximum frown has not returned to Baseline severity).

The Evaluating Investigator (i.e., Blinded Investigator) will be responsible for managing the subject, monitor for related and unrelated adverse effects, and carrying out the evaluations. Ideally, the same Evaluating Investigator will perform assessments for a given subject during the entire trial. Injections of study drug will be performed by an "Unblinded Injector" (i.e., physician or nurse practitioner appropriately skilled in injecting botulinum toxin into the glabellar area and not responsible for subject follow-up).

After exiting the study, subjects are eligible for a treatment of their glabellar lines at no cost provided that the investigator deems it appropriate.

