2. OVERVIEW OF STUDY DESIGN

2.1. Study Design

This is a multicenter, prospective, randomized, double-blind, active-controlled, single-treatment, increasing dose design.

Approximately 150 subjects will be randomized 1:1:1, to either 20U onabotulinumtoxinA, 20U prabotulinumtoxinA-xvfs, or 40U prabotulinumtoxinA-xvfs. Subjects with moderate or severe glabellar lines at maximum frown on the 4-point validated Glabellar Line Scale (*GLS*, 0=none, 1= mild, 2=moderate, 3=severe), as judged by the investigator and the subject, will be eligible.

Safety and effectiveness will be assessed on days 3, 7, and 30, then every 30 days up to 365 days or until the subject has returned to Baseline as assessed by the Investigator, at which point the subject will exit the study. Please refer to Table 1 below for visit specifics.

Duration of effect will be estimated by Kaplan-Meier analysis and will be based on the number of days from Treatment Day (Baseline) to the day that GLS severity (Investigator assessment) at maximum frown returns to the Baseline value (i.e., the treatment will be considered to remain effective for the amount of time during which GLS severity at maximum frown has not returned to Baseline severity).

The Evaluating Investigator (i.e., Blinded Investigator) will be responsible for managing the subject, monitor for related and unrelated adverse effects, and carrying out the evaluations. Injections of study drug will be performed by an "Unblinded Injector" (i.e., physician or nurse practitioner not responsible for subject follow-up).

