7. STATISTICAL METHODS

7.1. Primary Effectiveness Endpoint

The primary effectiveness endpoint will be duration of effect (regardless of responder status), defined as the number of days from Treatment Day (Baseline) to the day that GLS severity (Investigator assessment) at maximum frown returns to the Baseline value. Although the trial is not powered for inferential analysis, this will be the most influential outcome in the overall assessment of the effectiveness of prabotulinumtoxinA 40 Units, compared to prabotulinumtoxinA 20 Units, in treating moderate to severe glabellar lines. Analysis will be performed using the modified Intent-To-Treat (mITT) population and regardless of responder status.

Duration of effect will be described by Kaplan-Meier curves and the respective median times with associated 2-sided 95% confidence interval (CI) for each treatment group. Statistical analyses of treatment group differences will be done using Cox proportional hazards regression with time to return to Baseline as the dependent variable, treatment group as the independent variable, and age, gender, and Baseline GLS score (Investigator assessment) at maximum frown as covariates.

Statistical significance will be established at the 0.025 level with one-sided hypothesis testing.

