7.7. General Considerations

Data will be listed by subject number. Data will be summarized by treatment and study visit, where applicable. For categorical parameters, the number and percentage of subjects/observations in each category will be presented; percentages will be based on the number of subjects in the relevant analysis population in each treatment group. For continuous parameters, descriptive statistics will include n (number of subjects or observations), mean, standard deviation, median, and range. A full description of the statistical methods planned for this study will be provided in the Statistical Analysis Plan (SAP). All programs for data output and analyses will be written in SAS version 9.4 or higher (SAS Institute, Inc., Cary, NC).

Missing Values: For the mITT analysis of primary, secondary, tertiary, and exploratory duration of effectiveness endpoints, in the case of a missed visit, subjects will be considered to have returned to Baseline if they are confirmed to have returned to Baseline at the next non-missed visit. Subjects will be considered to have to have returned to Baseline if they fail to attend 2 consecutive visits or drop out of the study. For missing observations for exploratory endpoints other than duration of effect data will be analyzed as observed without imputation.

Discontinuation and Drop-Outs: Dropouts will not be replaced. Subject disposition will summarize the number of subjects who were randomized and who discontinued from the study (including reasons for discontinuation).

Interim Analysis: An interim analysis will be conducted when >90% of subjects have completed Visit 8 (Day 120) to evaluate response to exposure (efficacy, duration) and adverse events. For assessment of the primary effectiveness endpoint, 95% CIs will be presented but statistical analyses will not be conducted and a statistical penalty for the final analysis will not be employed. While data by treatment group will be presented, individual subjects will not be unblinded.

Poolability of Investigative Sites: Data from all investigative sites will be pooled based on the assumption of clinical comparability: the same protocol will be used for all sites, all sites will be monitored for protocol compliance, and the same data collection instrument and methodology will be used across all sites.

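### The stated 80% power at hazard ratio 0.47 does not match the planned 365-day follow-up, which gives about 86–89% power at 0.47 and 80% power at about 0.51–0.52

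*SAP*

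**What the plan says.** SAP 7.6 gives the basis of the calculation as "Assuming 50 subjects per treatment group, exponential distributions for failure and censoring times", adds a 4-month median in the reference group and a 10% annual censoring rate, and concludes that "the study will have 80% power to detect a hazard ratio of 0.47 based on a one-sided hypothesis test". The test is one-sided at alpha 0.025, which agrees with SAP 7.1: "Statistical significance will be established at the 0.025 level with one-sided hypothesis testing". Protocol 12.7 and the Sample Size entry of the protocol synopsis carry the same calculation.

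The figure is then used to justify the size of the trial: "As such, it is the opinion of the study Sponsor that 50 subjects per group (total sample size n=150) will be sufficient". SAP 7.6 and Protocol 12.7 also open by saying that the study is not powered for inferential analyses.

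None of the three places gives a follow-up time, an accrual pattern, an expected number of events or a formula. Follow-up appears only in the design sections. Protocol 4.1 has visits "then every 30 days up to 365 days or until the subject has returned to Baseline as assessed by the Investigator", SAP 2.1 says the same, and the synopsis gives a maximum of 379 days per subject (Day 365 plus its 14-day window). No calendar cut-off for the final analysis is stated.

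**The concern.** Power for a time-to-event comparison depends on the number of events, and under an exponential model that number depends on how long subjects are followed. The paragraph fixes every other input, so the stated power implies a follow-up time, and that time can be compared with the design. If the two disagree, the only quantitative support for 50 per group cannot be reproduced from the documents, and a reader is given the wrong hazard ratio as the effect detectable with 80% power.

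**Working it through.** **Inputs.** From SAP 7.6: n = 50 per arm, reference median 4 months, 10% annual censoring, one-sided alpha 0.025, hazard ratio (HR) 0.47. From SAP 7.1: the primary comparison is 40 U against 20 U of prabotulinumtoxinA, so two arms of 50. From SAP 2.1 and Protocol 4.1: 365 days, taken as 12 months per subject.

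**Hazards per month.**
- Reference: λ0 = ln 2 / 4 = 0.1733
- 40 U: λ1 = 0.47 × 0.1733 = 0.0814
- Censoring: c = −ln(0.9) / 12 = 0.0088

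**Expected events at 12 months.** P(event) = λ/(λ + c) × [1 − exp(−(λ + c) × 12)].
- Reference: 0.845, so 50 × 0.845 = 42.2 events
- 40 U: 0.597, so 50 × 0.597 = 29.8 events
- Total: about 72.1 events

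**Events that 80% power at HR 0.47 needs**, with z-values 1.960 + 0.842 = 2.802.
- Schoenfeld: 4 × 2.802² / (ln 0.47)² = 55.1, so 56
- Freedman: (2.802 × 1.47 / 0.53)² = 60.4, so 61

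**Power at HR 0.47 with 72.1 events.**
- Schoenfeld: √72.1 / 2 × 0.755 − 1.960 = 1.245, giving 89.3%
- Freedman: √72.1 × 0.53 / 1.47 − 1.960 = 1.101, giving 86.5%

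Reading 10% as a hazard of 0.10 per year changes either result by less than 0.1 percentage point.

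**Results by formula, 12 months, 50 per arm.** The last column is the follow-up at which the plan's own figure, 80% at 0.47, is reproduced.

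| Formula | Power at HR 0.47 | HR at 80% power | 40 U median at that HR (4/HR) | Follow-up giving 80% at 0.47 |
|---|---|---|---|---|
| Schoenfeld | 89.3% | 0.521 | 7.7 months | 6.9 months (211 days) |
| Exponential log-hazard (Wald) | 88.4% | 0.517 | 7.7 months | 7.6 months (231 days) |
| Hazard difference, pooled | 86.9% | 0.510 | 7.8 months | 7.9 months (239 days) |
| Freedman | 86.5% | 0.507 | 7.9 months | 8.2 months (249 days) |

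HR 0.47 itself implies a 40 U median of 4 / 0.47 = 8.5 months.

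**Simulation check.** Log-rank tests on simulated trials (40,000 per setting, Monte Carlo standard error about 0.2 points) with 12 months of follow-up and dropouts censored gave 89.5% at HR 0.47 with continuous event times and 89.2% with monthly visits. At HR 0.52 they gave 80.4% and 80.0%. With 7 months of follow-up, power at 0.47 was 79.8%.

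**Dropout rule.** The calculation censors dropouts, but SAP 7.7 treats subjects as "returned to Baseline if they fail to attend 2 consecutive visits or drop out of the study". Counting dropouts as events lowers simulated power at 0.47 to about 87% (a separate run of 3,000 trials gave 86%). This does not close the gap to 80%.

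**The case against.** The strongest reply is that no slip by the sponsor has been shown. The paragraph names no follow-up, and 80% at 0.47 is an ordinary result under some unstated choices: 7 to 8 months of follow-up per subject, or uniform accrual inside a 12-month calendar study (9.2 months of accrual by Schoenfeld, 7.1 by Freedman). That much stands. The sponsor may have computed correctly from an input it did not write down, but no such input appears in the documents, and both options conflict with following each subject to return to Baseline or Day 365.

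Two narrower points also reduce the gap without removing it. An unpooled hazard-difference formula gives 85.2% at 0.47, with 80% at 0.50; it is further from the planned Cox analysis than the log-hazard formulas, and it still does not give 80%. Protocol 11.3 aims for at least 135 evaluable subjects, or 45 per arm. With 45 per arm and 12 months, power is 82.7% (Freedman) to 86.0% (Schoenfeld), and 81.4% with the unpooled formula. The paragraph, however, assumes 50 per group and allows for censoring separately.

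Finally, the trial says it is not powered for inference, and the discrepancy is in the safe direction. Both are true and both limit the consequence. Neither corrects a figure that the same paragraph relies on to call the sample size sufficient.

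**Conclusion.** The concern holds and is minor. With the stated inputs and the planned 365 days per subject, power at HR 0.47 is about 86–89%, not 80%, and 80% power is reached at about 0.51–0.52. Expected events are 72, against 56 or 61 needed. The paragraph thus understates power by about 6 to 9 points and overstates the smallest effect detectable with 80% power: a 40 U median of 8.5 months, where 7.7–7.9 months would do.

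This rests on full 12-month follow-up for every subject not lost or returned to Baseline, 50 per arm, and the exponential model the plan itself assumes. If the sponsor assumed a shorter follow-up or a calendar cut-off, the 80% may be right, but the assumption is missing and differs from the design. The conclusion that 50 per group is sufficient is not weakened.

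**What to change.** In SAP 7.6, Protocol 12.7 and the synopsis, add the follow-up time and name one method, then give the figures that go with them. For example: *With 50 subjects per group, exponential failure and censoring times, a 4-month reference median, 10% annual censoring and 12 months of follow-up per subject, about 72 events are expected at a hazard ratio of 0.47, where power is 89% (Schoenfeld formula, one-sided alpha 0.025); 80% power is reached at a hazard ratio of 0.52.* If Freedman's formula is preferred, the figures are 86% and 0.51.

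If a shorter follow-up, or an accrual period with a calendar cut-off, was intended, state that assumption and keep 80% at 0.47.

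The cost is wording only.

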7.7. General Considerations

Data will be listed by subject number. Data will be summarized by treatment and study visit, where applicable. For categorical parameters, the number and percentage of subjects/observations in each category will be presented; percentages will be based on the number of subjects in the relevant analysis population in each treatment group. For continuous parameters, descriptive statistics will include n (number of subjects or observations), mean, standard deviation, median, and range. A full description of the statistical methods planned for this study will be provided in the Statistical Analysis Plan (SAP). All programs for data output and analyses will be written in SAS version 9.4 or higher (SAS Institute, Inc., Cary, NC).

Missing Values: For the mITT analysis of primary, secondary, tertiary, and exploratory duration of effectiveness endpoints, in the case of a missed visit, subjects will be considered to have returned to Baseline if they are confirmed to have returned to Baseline at the next non-missed visit. Subjects will be considered to have to have returned to Baseline if they fail to attend 2 consecutive visits or drop out of the study. For missing observations for exploratory endpoints other than duration of effect data will be analyzed as observed without imputation.

Discontinuation and Drop-Outs: Dropouts will not be replaced. Subject disposition will summarize the number of subjects who were randomized and who discontinued from the study (including reasons for discontinuation).

Interim Analysis: An interim analysis will be conducted when >90% of subjects have completed Visit 8 (Day 120) to evaluate response to exposure (efficacy, duration) and adverse events. For assessment of the primary effectiveness endpoint, 95% CIs will be presented but statistical analyses will not be conducted and a statistical penalty for the final analysis will not be employed. While data by treatment group will be presented, individual subjects will not be unblinded.

Poolability of Investigative Sites: Data from all investigative sites will be pooled based on the assumption of clinical comparability: the same protocol will be used for all sites, all sites will be monitored for protocol compliance, and the same data collection instrument and methodology will be used across all sites.

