### 10.2.5 Visits 5 to 15 (Visits each 30 Days; V5 $\pm$ 3 days, V6 to V15 $\pm$ 7 days)

Subjects will continue to be monitored for safety and effectiveness at one-month intervals. On and after **Day 90**, subjects are eligible to exit the study once their GLS score at maximum frown has returned to Baseline (Investigator assessment). Subjects will return for monthly assessments until they reach their Baseline GLS score (Investigator assessment). Assessment procedures include:

- Brow Area Photography
- Effectiveness Evaluations Investigator (Blinded Evaluator)
  - GLS (max frown)
  - GAIS
- Effectiveness Evaluations Subject
  - GLS (max frown)
  - GAIS
  - Subject Satisfaction
  - Clinical Interview (Visit 5; Day 30 only) (Section 10.3.4)
- Safety Assessments Investigator (Blinded Evaluator)
  - Directed Questionnaire
  - Directed Review of Systems
  - Vital Signs
  - Physical Exam
  - Concomitant Medications
  - Adverse Events

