7.4.3. Vital Signs

The number and percentage of subjects with a clinically significant vital sign abnormality (Investigator opinion) will be summarized for each parameter; percentages will be based on subjects with non-missing values.

Descriptive statistics will be used to summarize observed values and changes from Baseline. Tabular and graphical methods may be used to present results for parameters of interest. Listings will be provided with flags indicating clinically significant abnormalities.

7.4.4. 12-Lead ECGs

The number and percentage of subjects with a clinically significant ECG abnormality (Investigator opinion) will be summarized for each parameter; percentages will be based on subjects with non-missing values.

Descriptive statistics will be used to summarize results and changes from Baseline. Tabular and graphical methods may be used to present results for parameters of interest. Listings will be provided with flags indicating clinically significant abnormalities.

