14.4.5 Vital Signs

Table 14.4.5.1 Directed Questionnaire

	Pra	B 40	Pra	B 20	OnaB 20		
	(n =	= xx)	(n =	xx)	(n =	· xx)	
V1 (BL)	Yes	No	Yes	No	Yes	No	
Speaking	xx (x.x%)						
Swallowing	xx (x.x%)						
Breathing	xx (x.x%)						
Headaches	xx (x.x%)						
Eyelid Drooping	xx (x.x%)						
Eyebrow Drooping	xx (x.x%)						
V3 (48hr)							
Speaking	xx (x.x%)						
Swallowing	xx (x.x%)						
Breathing	xx (x.x%)						
Headaches	xx (x.x%)						
Eyelid Drooping	xx (x.x%)						
Eyebrow Drooping	xx (x.x%)						
V5 (D30)							
Speaking	xx (x.x%)						
Swallowing	xx (x.x%)						
Breathing	xx (x.x%)						
Headaches	xx (x.x%)						
Eyelid Drooping	xx (x.x%)						
Eyebrow Drooping	xx (x.x%)						
••••							
Speaking	xx (x.x%)						
Swallowing	xx (x.x%)						
Breathing	xx (x.x%)						
Headaches	xx (x.x%)						
Eyelid Drooping	xx (x.x%)						
Eyebrow Drooping	xx (x.x%)						

Shift from Baseline

(x.x%) = proportion of subjects

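### Three by-visit safety tables use the whole treated arm as denominator after subjects have exited, so percentages after Day 90 print too low and, if 40U lasts longer, unequally between arms

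*SAP*

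**What the plan says.** SAP 7.7 (repeated in Protocol 12.8) has data summarised by treatment and visit, and for categorical items "percentages will be based on the number of subjects in the relevant analysis population in each treatment group". SAP 7.5.3 defines the safety population, which "will consist of all randomized subjects who received treatment with the IP", so its size in each arm is the same at every visit.

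The SAP departs from that default in two places. In 7.4.3 (vital signs), and in the same terms in 7.4.4 (ECG), "percentages will be based on subjects with non-missing values". The antibody shell, Table 14.4.6.1, carries its own n at each visit.

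The Directed Questionnaire, Directed Review of Systems and Physical Exam shells are also laid out by visit. They show one n per arm in the column header and none per visit, and their footnotes call the percentage only a proportion of subjects. No text in SAP 7.4 gives them a different denominator. The missing-value paragraph in 7.7 deals with effectiveness endpoints only.

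On exit, SAP 2.1 has follow-up continue "until the subject has returned to Baseline as assessed by the Investigator, at which point the subject will exit the study". Protocol 10.2.5 places this on or after Day 90, when "subjects are eligible to exit the study once their GLS score at maximum frown has returned to Baseline".

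**The concern.** All three assessments are made at each clinic visit, and only in subjects still in the study. Once subjects begin to exit for loss of effect, the 7.7 denominator includes people who could not be asked or examined. The printed percentage is then the rate among those assessed multiplied by the share of the arm still attending.

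That share falls with time, and its fall is tied to the primary endpoint. If 40U works longer, more of that arm is still present at each late visit, and its printed percentage is higher for that reason alone. Safety of 40U is a primary objective (SAP 1.4), and SAP 6.1 says the questionnaire looks for signs of local or distant toxin spread. A reader who compares arms on these percentages could see a dose difference that is only a difference in attendance, and would see late rates that are too low in every arm.

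**Working it through.** **The plan's own figures.** The plan states no by-visit safety rate, so there is none to reproduce. Its one computed figure, 80% power at a hazard ratio of 0.47 (SAP 7.6), serves here only as a source of assumptions and is not disputed. For the record, with 50 per arm all followed 12 months I get 42.2 + 29.8, about 72.1 events, and 89.3% power (Schoenfeld, one-sided 0.025). Staggered entry over nine months within a 12-month total gives 55.6 events and 80.4%. The documents state no accrual pattern.

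**Inputs.** From SAP 7.6: 50 per arm, exponential times, 4-month reference median (taken as 120 days), 10% annual censoring, HR 0.47. From Protocol 10.2.5: exit from Day 90. My assumption, for illustration: 10% of attending subjects in both arms report a symptom. The ratios do not depend on it.

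**Formulas.** If the visit at which return is found is tabulated in its nominal row, a subject appears in a given row when there was no return by the previous visit, day *t*:

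- attendance = 2^(−HR·t/120) × 0.9^(t/365), with HR = 1 for 20U
- printed % = rate among attenders × attendance
- printed ratio, 40U to 20U, at equal true rates = 2^((1−HR)·t/120). Dropout cancels.

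**Day 180 (t = 150).**

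- 20U: 2^(−1.25) × 0.9^(150/365) = 0.420 × 0.958 = 0.403
- 40U at HR 0.47: 2^(−0.5875) × 0.958 = 0.665 × 0.958 = 0.637
- Understatement in the 20U arm: 1 − 0.403, about 60%
- A true 10% in both arms prints as 4.0% vs 6.4%, ratio 2^0.6625 = 1.58

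| Visit | Attending, 20U | Attending, 40U (HR 0.47) | Printed, true 10% | Ratio |
|---|---|---|---|---|
| Day 120 | 58% | 76% | 5.8% vs 7.6% | 1.3 |
| Day 180 | 40% | 64% | 4.0% vs 6.4% | 1.6 |
| Day 270 | 23% | 49% | 2.3% vs 4.9% | 2.1 |

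**Sensitivity at Day 180.**

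- Effect size: HR 0.7 gives 2^0.375 = 1.30, HR 0.85 gives 2^0.1875 = 1.14, and HR 1.0 gives 1.00. At HR 1.0 every arm is still understated by about 60%.
- Visit mapping: if exit visits are stored under Visit 16, the Day 180 row holds only subjects with no return by Day 180. The ratio is then 2^(0.53 × 1.5) = 1.73 at HR 0.47 and 2^(0.3 × 1.5) = 1.37 at HR 0.7. Months of 365/12 days change these figures only in the second decimal.
- Shape: a Weibull with shape 2 and the same median gives attendance of 34% vs 60% before dropout at HR 0.47, a ratio of about 1.8.

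**With the visit denominator.** The same inputs print 10% vs 10% at every visit, whatever the hazard ratio.

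**The case against.** The strongest reply is that only a percentage is wrong and the tables let a reader repair it. This stands. Yes and No counts are both printed in Table 14.4.5.1, so their sum is the number assessed. The two shift tables have a Total row and a Total column at each visit, and the cell where they meet is the number assessed. Table 14.1.4 gives attendance by visit and arm. Yes and No percentages that fail to reach 100% would also alert a careful reader.

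The numbers behind the percentages are small. At Day 180 a 10% rate means about 2.0 vs 3.2 subjects (50 × 0.403 × 0.10 and 50 × 0.637 × 0.10). The summaries are descriptive, these shells carry no between-arm p-values, and problems recorded as adverse events also appear in the cumulative tables.

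Several wider readings are tempting, and the documents do not support them:

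- *All by-visit safety percentages are affected.* Vital signs, ECG and antibodies are protected. The laboratory shift shell has only a final-visit row, and exiting subjects have laboratory tests at that visit (Protocol 10.2.6). Adverse event incidence is cumulative, not by visit.
- *Departed subjects are recorded as symptom-free.* They fall in neither the Yes nor the No column.
- *40U will look less safe.* That needs 40U to retain more subjects, and HR 0.47 is the effect detectable at the stated power, not a forecast.
- *The distortion is greatest at Day 365.* Visit 16 is also the final or early termination visit. If all exits are tabulated there, that row holds nearly everyone. The documents do not settle the mapping, so no Day 365 figure is given here.

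What the reply does not remove is that SAP 7.7 states a rule and, for these three tables, following it prints a percentage that does not describe the subjects assessed.

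**Conclusion.** The point holds for Tables 14.4.2.3, 14.4.3.1 and 14.4.5.1, at visits after Day 90 under Protocol 10.2.5. Earlier rows are affected only by dropout and missed visits. Percentages are understated in all arms, by about 60% in a 20U arm at Day 180. Between arms the distortion is conditional on a difference in duration: the Day 180 ratio is about 1.6 at HR 0.47, about 1.3 at HR 0.7, and 1.0 if duration does not differ.

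These sizes rest on the plan's exponential model, 4-month median and 10% annual censoring, and on subjects leaving as soon as they may. If some eligible subjects stay, the effect is smaller. SAP 2.1 and the Table 1 footnotes in both documents give no Day 90 limit on exit. Those passages and Protocol 10.2.5 must be reconciled, since the point at which attendance begins to fall depends on them.

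Severity is low: counts are right, the visit n can be recovered, and the error is confined to the printed percentages.

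**What to change.** In SAP 7.7 or 7.4, state that for Tables 14.4.2.3, 14.4.3.1 and 14.4.5.1 the percentage at each visit is based on subjects with a non-missing assessment at that visit, the convention 7.4.3 and 7.4.4 already use. Print that n for each visit and arm, as Table 14.4.6.1 does. State as well whether assessments at an early exit visit are tabulated under their nominal visit or under Visit 16.

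The cost is a sentence or two and a visit-level n in three shells, with no new data. The small downside is that late percentages will rest on small, shrinking denominators, about 20 vs 32 subjects at Day 180 at HR 0.47. Printing the n makes this visible.
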